5. GENERAL STATISTICAL CONSIDERATIONS

5.1. General Presentation of Summaries and Analyses

Continuous variables will be presented by descriptive statistics: n, mean, standard deviation (standard error, as needed), median, minimum, and maximum. Categorical variables will be presented by counts of patients and percentage. Unless otherwise specified, the denominator for all percentages will be the number of patients in the population of interest. For plasma concentrations and PK variables, coefficient of variation (CV%) and geometric mean will be additionally provided.

Any p-values will be rounded to four decimal places and will be presented as '<.0001' if they are less than 0.0001 after rounding.

For continuous variables that are recorded as "< X" or "> X", the value of "X" will be used in the calculation of summary statistics. The original values will be used for the listings.

In this study, eGFR will be calculated by the central lab using the Cockcroft-Gault (CG) formula as described in protocol Appendix L.

Decimal points will be presented as follows: N will be presented without decimal, CV with one decimal, minimum/maximum in same precision as in the database, mean/median in one more decimal than minimum/maximum, and SD in one more decimal than mean/median.

Analyses will be conducted using SAS® Version 9.3 or higher. All tables and listings will have a header showing "FibroGen, Inc." and the protocol number. A footer will show the program file name and path, run date, run time, and output file name and path.

The secondary endpoints will be tested sequentially, the family-wise type I error rate will be controlled using the method described in [Section 12.1](#).

All individual data will be presented in individual patient data listings.

Data from the open-label and double-blind component of the study will be analyzed separately. Patients enrolled in open-label component may remain in the study up to 52 weeks and will undergo all procedures as will the randomized patients (except Health-Related Quality of Life (HRQoL) assessments including PROMIS and EQ-5D-5L), but the data will be included in the analysis of open-label component only.

For the double-blind component, data will be analyzed for the first 28 weeks of treatment and for the end of the 52-week study treatment period respectively.

Patients from the OL high-erythropoietin component will undergo the same procedures as will patients from the OL component with the exception of completing the HRQoL questionnaires. Data from the OL high-erythropoietin component will be analyzed along with the OL component. HRQoL data from the OL high-erythropoietin component will be listed. The final analysis will be done for the end of the 52-week study treatment period.

5.2. Analysis Population for Open-Label Component and OL High-Erythropoietin Component

5.2.1. Full Analysis Set (FAS)

The full analysis set consists of all patients enrolled into this study who receive at least one dose of study medication, and at least one corresponding on-treatment Hb assessment.

5.2.2. Safety Analysis Set (SAF)

The safety analysis set consists of all patients who have received at least one dose of study drug. Analyses of the safety data will be based on the safety analysis set.

5.3. Analysis Population for Double-Blind Component

5.3.1. Full Analysis Set (FAS)

The full analysis set consists of all patients randomized to this study who receive at least one dose of study medication, and at least one corresponding on-treatment Hb assessment. Patients will be included in the treatment group to which they are randomized for the FAS analysis.

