### 6.3.1 Study Procedures and Assessments by Visit

#### 6.3.1.1 Study Procedures and Assessments to be Done at All Study Visits

The following will be done at ALL study visits within the Treatment and Follow-Up Periods:

- Recording of transfusions
- Central CBC with Hb level and WBC differential
- Local hemoglobin level (hemocue device is encouraged but not required)
- Review and record AEs
- Review and record concomitant medications, procedures and non-drug therapies
- Review hemoglobin level for any dose adjustments that are deemed necessary ([Appendix C](#) and [Appendix D](#))
- Ensure patient dosing compliance

Local laboratory testing of Hb for dose adjustment decisions will be done at the Local level – use of the Hemocue device is encouraged but not required. Central laboratory values of Hb will be used for all data analysis purposes

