### 6.3.1.2 Additional Study Procedures/Assessments and Blood Sampling by Visit

Table 2 below lists additional study procedures/assessments and blood sampling by visit for the 52-week Treatment Period, EOT and Post-EOT.

All blood samples must be drawn prior to dose unless otherwise noted (e.g. certain PK draws).

**Table 2 Additional Study Procedures/Assessments and Blood Sampling by Visit for the 52-Week Treatment Period, EOT and Post-EOT (Appendices A, B, K)**

Study Visit	Procedures and Assessments	Blood Samples
Day 1 (Week 1)	
 
• Inclusion/Exclusion criteria verification/review (including documentation of MDS)
 
• ECOG score
 
• Weight
 
• Vital signs (BP, HR, RR, and Temp) immediately prior to the time of the PK sampling
 
• Health-related quality of life (HRQoL) assessments
 
• Review and record baseline conditions, AEs, if any (capture the event under medical history, if applicable)
 
• Register/Randomize patient (dose confirmation)
 
• Dispense study drug
 
• Dose patient (first dose should be given at the site)
 
	
 
• Serum chemistries
 
• Serum lipid panel
 
• LFTs
 
• Iron biomarkers
 
• PT and PTT
 
• Heparin
 
• C-reactive protein
 
• Serum pregnancy (for females of childbearing capability)
 
• Endogenous serum EPO level
 
• PK samples 1-3 and 3-5 hours after dosing
 
• CBC (central) and Local Hb
 

Week 2		
 
• CBC (central) and Local Hb
 

Week 3	
 
• Dispense study drug
 
	
 
• LFTs
 
• CBC (central) and Local Hb
 

Week 4		
 
• CBC (central) and Local Hb
 

Week 5	
 
• Vital signs (BP, HR, RR, and Temp) at the time of PK sampling
 
• ECOG score
 
• Dispense study drug
 
	
 
• Serum chemistries
 
• Serum lipid panel
 
• LFTs
 
• Iron biomarkers
 
• Heparin
 
• Endogenous serum EPO level
 
• Reticulocytes & CHr
 
• PK sample 4-6 hours after dosing
 
• CBC (central) and Local Hb
 

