16. Study drug dosing: begins on the first day of dosing (Day 1/Week 1). All study procedures must be completed prior to administration of the 1st dose of study treatment. Dosing should occur at approximately the same time of day. Roxadustat/placebo (study medication) can be taken with water with or without food. The dose of statins should not exceed the protocol-recommended daily dose in the protocol.
17. Last dose of study drug must be prior to EOT assessments
18. Dose adjustment review every 8 weeks for upward adjustments. Week 9 evaluation requires determination of Erythroid Response. A re-assessment will be done for these patients at Week 12 and if TI is observed the dose will not be increased.
19. Must be at least 28 days post-dose/EOT

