5.7. Other Key Definitions and Computations

Study Day

Study day will be calculated in reference to the date of the first dose (Study Day 1, which refers to the enrollment/randomization in the protocol). For assessments conducted on or after the first dose date, study day is calculated as (assessment date – first dose date + 1). For assessments conducted before the first dose date, study day is calculated as (assessment date – first dose date). There will be no Study Day 0.

In the listings, study days will be presented along with assessment date where applicable.

Date of First Dose and Date of Last Dose of Study Drug

The date of the first dose of study drug is defined as the date a patient receives the first dose of study drug (roxadustat or placebo). The date of the last dose of study drug is defined as the date a patient receives the last dose of study drug (roxadustat or placebo).

Treatment Day

Treatment day will be calculated in reference to the date of the first dose of study drug. Treatment Day 1 corresponds to the date a patient receives the first dose of study drug. For assessments conducted on or after the date of the first dose of study drug, treatment day will be calculated as (assessment date – date of first dose of study drug + 1). There will be no Treatment Day 0.

Treatment Period

The treatment period is defined as the period of time from the date and time of the first dose of study drug through the date of last dose.

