12.3. Analysis of Double-Blind Efficacy Endpoints

12.3.1. Analysis of Primary Efficacy Endpoint

The primary efficacy endpoint for this study is proportion of patients who achieved TI ≥ 56 consecutive days (e.g., 8 weeks) since first dose in the first 28-week of treatment. TI is defined as the absence of any intravenous RBC transfusion (packed cell or whole blood) during any consecutive 56 days during the treatment period (e.g., Days 1 to 56, Days 2 to 57, Days 3 to 58). All RBC transfusions from 8 to 16 weeks prior to first dose until end of study will be recorded on CRF. TI will be estimated in the duration beginning with the first dose date (Day 1) and ending with the date of end of treatment or last visit date at

week 28, whichever comes earlier. RBC transfusions after end of treatment will be recorded on the CRF until the last visit at week 52 from first dose but will not be used to define TI.

The endpoint will be also analyzed for the end of the 52-week study treatment period as a secondary endpoint.

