12.3.1.1. Primary Analysis

The RBC TI response rate and its two-sided 95% confidence interval based on the exact method of Clopper-Pearson will be presented in a frequency table by treatment group using the FAS.

The primary objective of the study will be evaluated to demonstrate a statistically significant difference between roxadustat and placebo group with respect to the RBC transfusion independence rate based on the Cochran-Mantel-Haenszel (CMH) chi-square test adjusting for the stratification factors (EPO level, IPSS-R risk category and RBC transfusion burden). A CMH-adjusted odds ratio (roxadustat versus placebo) and its associated 95% CI will be computed to compare between the roxadustat group and placebo group.

This analysis will take into account the potential intercurrent events as follows:

1. Treatment discontinuation (such as: due to Disease progression, Liver function, Patient decision, Investigator decision, AE/SAE, etc.): using while on treatment strategy: Patients who have discontinued treatment early for any reasons prior to week 8 will be classified as non-responders. For patients who have discontinued treatment early for any reasons after week 8, TI will be estimated in the duration beginning with the first dose date (Day 1) and ending with the date of end of treatment or last visit date at week 28, whichever comes earlier.
2. Death: using While on treatment strategy: Treatment effect while on treatment is of interest. Patients who died prior to week 8 will be classified as non-responders. For patients who died after week 8, the RBC TI response will be based on RBC transfusion records up to the date of end of treatment or last visit date at week 28 or death, whichever comes earlier.

The number of periods of 8 weeks (56 consecutive days) that meet the criterion of TI per TI responder will be summarized descriptively.

Hypothesis testing:

The odds ratio (OR) in treatment response (roxadustat vs. placebo) is given by:

$$OR = (n_1 * (N_2 - n_2)) / (n_2 * (N_1 - n_1))$$

Where:

N_1 = the number of patients in roxadustat group

N_2 = the number of patients in placebo group

n_1 = the number of patients who achieved TI \geq 56 consecutive days (e.g., 8 weeks) since first dose in the first 28-weeks of treatment in roxadustat group

n_2 = the number of patients who achieved TI \geq 56 consecutive days (e.g., 8 weeks) since first dose in the first 28-weeks of treatment in placebo group

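### The double-blind FAS requires an on-treatment Hb that the primary endpoint does not use, so some early non-responders can leave the denominator, and no all-randomized analysis is pre-specified

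*SAP*

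**What the plan says.** - **Analysis set.** SAP 5.3.1 admits "all patients randomized to this study who receive at least one dose of study medication, and at least one corresponding on-treatment Hb assessment", analysed as randomized. SAP 12.3.1.1 presents the primary response rates on this set, alongside the confirmatory stratified CMH test.
- **Endpoint.** SAP 12.3.1: "TI is defined as the absence of any intravenous RBC transfusion (packed cell or whole blood") over any 56 consecutive days of the treatment period. The data source is the transfusion record on the CRF.
- **Early stop or death.** SAP 12.3.1.1: "Patients who have discontinued treatment early for any reasons prior to week 8 will be classified as non-responders", and likewise "Patients who died prior to week 8 will be classified as non-responders".
- **What on-treatment might mean.** SAP 5.7 defines the treatment period as running "from the date and time of the first dose of study drug through the date of last dose". SAP 19.3.1 (Tables 7.1 and 7.6) opens the first post-baseline window on Day 1 after dosing and treats assessments as follow-up only from the follow-up visits onward. Neither section says which reading applies in 5.3.1.
- **Other planned analyses of the primary endpoint.** Sensitivity Analysis 1 uses the per-protocol set, which needs at least 8 weeks of treatment (5.3.3). Sensitivity Analysis 2 uses the FAS. The analysis in 5.6 swaps randomized for actual strata. Further analyses for differential early discontinuation are optional, and their population is not named.
- **Reporting.** SAP 6.2 counts patients randomized but not treated and the size of each set, and 19.9 includes a listing of analysis populations.

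**The concern.** Two rules in the same plan treat one kind of patient differently. Someone who takes a dose and then stops or dies before a qualifying Hb is a non-responder by the response rule, but is outside the set to which that rule is applied. The exclusion is made after randomization and depends on events after dosing. Almost everyone excluded this way would have counted as a non-responder, so removing them raises the rate in any arm that loses one. The condition gives the primary analysis nothing in return, because no Hb value enters the endpoint.

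What is at stake is the strength of the intention-to-treat claim for test 1, and for test 2, which is the same endpoint over 52 weeks. A reader could rebuild crude all-randomized rates from the disposition table and the listing. The stratified test and odds ratio in all randomized patients are not pre-specified, and if they were added after unblinding they would carry less weight.

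**Working it through.** **1. The plan's own figures.** SAP 3.2 claims at least 90% power for a two-sided Fisher exact test at 0.05. Exact enumeration over two binomials gives 99.9% for 72:48 at 56% vs 13% and 99.9% for 96:64 at 35% vs 5%. Both claims hold with a wide margin.

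**2. Who can be excluded.** Day 1 blood does not count, because "All blood samples must be drawn prior to dose unless otherwise noted (e.g. certain PK draws". The first post-dose Hb can be the Week 2 or Week 3 draw, or the end-of-treatment draw of an early stopper. Protocol 6.3.1.1 lists central and local Hb under "The following will be done at ALL study visits within the Treatment and Follow-Up Periods". There are two readings:
- *Windows (SAP 19.3.1).* Any Hb from Day 1 post-dose until follow-up counts. The Week 2 window runs from then to scheduled day 8 + 3 = day 11 (Table 7.6). The Week 3 window runs to before scheduled day 15 + 7 = day 22 (Table 7.1). An early end-of-treatment Hb falls inside, so only a dosed patient with no Hb at all before follow-up is lost.
- *Treatment period (SAP 5.7).* The period closes on the date of last dose, and Protocol Appendix A footnote 17 says "Last dose of study drug must be prior to EOT assessments". An end-of-treatment Hb on a later date would not count; one on the same date would.

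**3. Inputs for the size.** SAP 17 gives 140 enrolled patients. The 84:56 split is my assumption (exact 3:2). The planned rates are 56% vs 13% and 35% vs 5% (SAP 3.2); the nearest counts used are 47/84 vs 7/56 and 29/84 vs 3/56. The number excluded is not in the documents, so I take 1 to 3 from one arm, all non-responders. Stratum counts are not given, so I use the CMH statistic with a single stratum:

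χ² = (x − n₁r/N)² ÷ [n₁n₂r(N − r) / (N²(N − 1))], where x is roxadustat responders, r is all responders and N = n₁ + n₂.

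For 47/84 vs 7/56: r = 54 and x − n₁r/N = 47 − 84×54/140 = 14.6. The variance is 84×56×54×86/(140²×139) = 8.018. So χ² = 213.16/8.018 = 26.58 and p = 2.5×10⁻⁷.

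**4. Results at the planned effects.**

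| Counts | Difference (points) | Shift | p |
|---|---|---|---|
| 47/84 vs 7/56 | 43.5 | – | 2.5×10⁻⁷ |
| 47/81 vs 7/56 | 45.5 | +2.1 | 9.2×10⁻⁸ |
| 47/84 vs 7/53 | 42.7 | −0.7 | 6.8×10⁻⁷ |
| 29/84 vs 3/56 | 29.2 | – | 6.0×10⁻⁵ |
| 29/81 vs 3/56 | 30.5 | +1.3 | 3.7×10⁻⁵ |
| 29/84 vs 3/53 | 28.9 | −0.3 | 1.1×10⁻⁴ |

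Losing significance would take 35 dropped placebo non-responders in the first case (47/84 vs 7/21, p = 0.065) and 34 in the second (29/84 vs 3/22, p = 0.059).

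**5. Near the boundary.** I scanned every roxadustat count above the placebo rate, dropping 1 to 3 from one arm.
- Placebo 7/56: the result flips only at 22/84 (p = 0.051, or 0.047 with one roxadustat patient dropped) and at 23/84 (p = 0.036, or 0.052 with three placebo patients dropped).
- Placebo 3/56: it flips only at 14/84 (p = 0.046, or 0.053 with two placebo patients dropped).

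Enumerating all outcomes at 84:56, the chance of landing where such a flip is possible is 0.03% at 56% vs 13% and 0.3% at 35% vs 5%, even if the exclusions do occur.

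**The case against.** **An early stopper's end-of-treatment Hb counts.** A reader might infer from SAP 5.7 and footnote 17 that it never does. The documents do not support that as a general statement. The 19.3.1 windows accept any Hb from Day 1 post-dose until follow-up, and even under 5.7 a sample on the day of the last dose is inside the period. SAP 5.4 also allows a local value to replace a missing central one in Hb efficacy summaries. This stands: the wording needs a definition, but on the windows reading very few patients are affected.

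**Set first, rule second.** It can be argued that defining a set and then classifying responses within it is no contradiction. That is formally true, and every patient with one post-dose Hb who stops before week 8 is still counted as a non-responder. It does not explain why an endpoint built on transfusions needs an Hb to enter the set.

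**Unseen text.** The SAP follows protocol Amendment 03, which is not supplied. The supplied Amendment 02 (section 8.2.1) defines the FAS as all randomized patients, and a reader might infer an undeclared change. That cannot be concluded: Amendment 03 may carry the new definition, and the supplied list in SAP 17 starts at item 3. SAP 19.9 also names a Sensitivity Analysis III that the text does not describe. The statement is therefore limited to the supplied SAP text.

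**Never-dosed patients should be rare.** Randomization is on Day 1 before a first dose given at the site, and treatment is blinded. This stands, and it makes the dose condition the lesser issue.

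**Conclusion.** The point holds as a defect of definition with a probably small effect. SAP 5.3.1 makes the confirmatory set depend on a measurement that the primary endpoint does not use. It can remove patients whom 12.3.1.1 would call non-responders, and nothing in the supplied SAP text restores all randomized patients.

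Three stronger inferences are not supported:
- **That the rule favours roxadustat.** The direction depends on which arm loses patients. Equal numbers do not cancel exactly: three from each arm at 47/84 vs 7/56 gives a net +1.4 points. The documents give no exclusion counts.
- **That the trial's conclusion is at risk.** At either planned effect it is not; only a result near p = 0.05 could change.
- **That the whole testing hierarchy needs rebuilding.** The argument concerns the transfusion-independence endpoint in tests 1 and 2.

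The size rests on an assumed 84:56 split, at most three exclusions from one arm, all of them non-responders, and an unstratified calculation. The change is worth making because it costs little and is most credible before unblinding.

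**What to change.** 1. In SAP 5.3.1, delete the on-treatment-Hb condition for the primary endpoint (tests 1 and 2).
2. Pre-specify one stratified CMH test and odds ratio of the primary endpoint in all randomized patients, as randomized. Count as non-responders those never dosed and all who stop or die before week 8.
3. Keep the dosed-with-Hb set, under its own name, for Hb summaries, and state there whether on-treatment follows the 5.7 period or the 19.3.1 windows.

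The other secondary tests need no redesign. The cost is SAP wording and one extra table. No new data are collected, and response rates may fall slightly.

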5.3.2. Safety Analysis Set (SAF)

The safety analysis set consists of all patients who are randomized to this study and have received at least one dose of study drug. Analyses of the safety data will be based on the SAF. Patients will be included in the treatment group based on treatment they actually received.

5.3.3. Per-Protocol Set (PPS)

The Per-Protocol Set (PPS) consists of patients who have received at least 8 weeks of treatment with corresponding on-treatment Hb assessments and are without major protocol deviations that affect the assessment of study endpoints. The PPS population will be used for supportive and/or sensitivity analyses of the efficacy endpoints.

5.4. Methods of Data Transformation and Handling of Missing Data

All data collected and recorded in the study database will be eligible for inclusion in the analysis. No substitutions for missing data will be made unless otherwise specified in this SAP, except for dates that occur prior to a patient being enrolled in the study (e.g., medications received before screening). For these date imputations, refer to [Appendix 19.3](#).

Some lab data are collected using local labs (in lieu of the ICON central lab) due to central lab kit shortages caused by the COVID-19 pandemic. In these cases, local lab values and reference ranges collected from CRFs will be presented in the listings along with central lab data when appropriate and feasible. Local lab values will be flagged in datasets and data listings to be differentiated from central lab values. For summary analyses of Hemoglobin efficacy and laboratory safety in tables and figures, if central lab is not available at a scheduled visit and local lab is available, the local lab will be used for substitution.

5.5. Baseline Measures and Change from Baseline

For patients who achieved $\geq 50\%$ reduction in number of pRBC transfusions over any 8 weeks (day 1 to week 52) compared to their baseline, the baseline will be calculated based on the transfusions within 8 or 16 weeks prior to the first dose.

For subjects with transfusion records within 16 weeks prior to first dose: Baseline number of transfusions (pRBC/8-weeks) = total number of packs of red blood cells within 16 weeks prior to first dose/2.

For subjects with transfusion records within only 8 weeks prior to first dose: Baseline number of transfusions (pRBC/8-weeks) = total number of packs of red blood cells within 8 weeks prior to first dose.

For other measurements, baseline value will be defined as the last measure taken before any study drug administration unless otherwise specified.

Change from baseline is defined as the difference between the baseline value obtained and the respective post-baseline time point for the continuous variables. Negative values represent decreases from baseline; positive values reflect increases from baseline.

Percent change from Baseline is defined as the change from Baseline divided by the Baseline value, multiplied by 100:

$$100 \times (\text{Post-Baseline value minus Baseline value}) / (\text{Baseline value})$$

